 - 7.2 Safety Monitoring Plan
 - 7.2.1 Anticipated Risks / Risk Mitigation
 - 7.2.2 Medical Monitoring for Participant Safety
 - 7.2.3 Study Stopping Rules
 - 7.3 Anticipated Adverse Events
 - 7.4 Adverse Event Reporting
 - 7.4.1 Adverse Events
 - 7.4.2 Serious Adverse Events
 - 7.4.3 Unanticipated Adverse Device Effects
 - 7.4.4 UPIRTSO Events
 - 7.5 Data Safety Monitoring Board
- 8. Data Handling and Record Keeping
 - 8.1 Confidentiality
 - 8.2 Source Documents
 - 8.3 Case Report Forms
 - 8.4 Clinical Reports
 - 8.5 Records Retention
- 9. Study Monitoring, Auditing, and Inspecting
 - 9.1 Study Monitoring Plan
 - 9.2 Quality Assurance Procedures
- 10. Ethical Considerations
- 11. Study Finances
 - 12.1 Funding Source
 - 12.2 Conflicts of Interest
- 12. Publications Plan
- 13. References
- 14. Appendices and Attachments

Study Summary

Title	Repetitive Transcranial Magnetic Stimulation in Spasmodic	
	Dysphonia	
Short Title	rTMS in Spasmodic Dysphonia	
Protocol Numbers	CTSI 25008	
Study Sponsor	Minnesota's Discovery, Research and InnoVation Economy, Dept.	
	Rehabilitation Medicine, Division of Physical Therapy	
Principal Investigator	[name]	
Study Design	Pilot study: 2 groups, pre/post test design	
Study Duration	24 months	
Study Center(s)	CTSI	
Objectives	The overall purpose of this study is to test whether brain excitability	
	can be modulated in people with spasmodic dysphonia (a neurological	
	disorder affecting the vocal folds) using repetitive transcranial	
	magnetic stimulation (rTMS). More specifically, the study objectives	
	include: (1) Determine safety and feasibility of the proposed protocol;	
	(2): Determine amount of intracortical inhibition in the laryngeal	
	motor cortex as measured in the thyroarytenoid muscle both within	
	and between groups, before and after rTMS; (3) Explore changes in	
	voice quality following rTMS.	
Number of Subjects	Fifty participants will be enrolled.	
Main Inclusion /	Primary inclusion for spasmodic dysphonia:	
Exclusion Criteria	(1) 21-75 years of age	
	(2) Diagnosis of adductor spasmodic dysphonia	
	(3) Symptoms at worst severity if receiving regular botulinum	
	injections	
	Primary exclusion for participants with spasmodic dysphonia:	
	(1) Other forms of dystonia	
	(2) Vocal fold pathology or paralysis	
	(3) Diagnosis of voice tremor	
	(4) Laryngeal surgery	
	(5) Laryngeal cancer or neurological condition other than dystonia	
	(6) Contraindication to TMS(7) Medications with effect on CNS	
	(8) Inability to complete tasks associated with study(9) Adult lacking ability to consent	
	(3) Addit facking ability to consent	
	Primary inclusion for healthy participants (controls):	
	(1) 21-75 years of age	
	(2) Absence of vocal fold pathology	
	(2) Hoseinee of vocal fold pathology	
	Primary exclusion for healthy participants (controls):	
	(1) Any health condition or disability that would interfere with	
	participation	
	paraorpanon	

	(2) Contraindications to TMS	
	(3) Medications with effect on CNS	
	(4) Adult lacking ability to consent	
Study Device	Device: Magstim 200 ² and Rapid ² Magnetic Stimulators and Magstim	
	BiStim Module	
	Manufacturer: Magstim Company LTD, Spring Gardens	
	[name]	
	US Distributor: Jali Medical, Inc.	
	[name]	
	[name]	
Duration of Device	Each subject will receive a 20 minute session of low-frequency rTMS	
Exposure	(1Hz, 1200 pulses). Single pulse TMS testing also will be applied for	
	approximately 30 min before and after rTMS.	
Reference Therapy	None	
Endpoints	Corticospinal excitability and voice quality will be measured before	
	and after rTMS application. Self-reported voice disability also will be	
	assessed.	
Statistical Methods	Corticospinal excitability and voice quality will be examined for	
	effects of rTMS and group.	

List of Abbreviations

AdSD Adductor spasmodic dysphonia

AE Adverse Event BTX Botulinum Toxin

CFR Code of Federal Regulations

CRF Case Report Form

DSMB Data and Safety Monitoring Board DSMP Data and Safety Monitoring Plan

EMG Electromyography

FDA Food and Drug Administration

GCP Good Clinical Practice

HIPAA Health Insurance Portability and Accountability Act of 1996

ICH International Conference on Harmonization

IRB Institutional Review Board PHI Protected Health Information

rTMS Repetitive Transcranial Magnetic Stimulation

SAE Serious Adverse Event

TMS Transcranial Magnetic Stimulation
UADE Unanticipated Adverse Device Effect

UPIRTSO Unanticipated Problems Involving Risk To Subjects or Others

1.3 Key Study Personnel

NA

2.0 Introduction

2.1 Background and Rationale

Focal dystonia is a neurological movement disorder characterized by excessive involuntary muscle contractions of any body part, severely impairing a person's ability to function in their daily life. Often patients are misdiagnosed and receive years of unnecessary treatment. Adductor spasmodic dysphonia (AdSD) is the primary form of laryngeal dystonia and is characterized by excessive contraction of intrinsic muscles in the larynx, leading to intermittent hyper-adduction of the true vocal folds ('vocal cords') during speech (Aminoff *et al.*, 1978). This results in severe difficulty in speaking, hindering effective communication and severely reducing quality of life.

The cause of AdSD is unknown and there are no treatments that produce long-term benefits. Neuroimaging and neurophysiology studies have suggested that AdSD and other focal dystonias are associated with decreased inhibition and excessive plasticity in sensorimotor areas in the brain (Kimberley *et al.*, 2009; Kimberley and Pickett, 2012; Kimberley *et al.*, 2013; Kimberley *et al.*, 2015a; Samargia *et al.*, 2016). However, to our knowledge, no studies have investigated the effects of modulating excitability of the laryngeal motor cortex in healthy individuals or AdSD. This gap in the field is likely due to challenges in recording corticospinal excitability of intrinsic laryngeal muscles.

[name] team has developed a transcranial magnetic stimulation (TMS) method to assess the cortical representation and excitability of the thyroarytenoid, a muscle affected in AdSD. Using this method, TMS data indicate differences in inhibition in people with AdSD vs. healthy controls. For this pilot project, we propose to further explore this excitability difference by investigating the effects of low-frequency inhibitory repetitive TMS (rTMS) applied to the laryngeal motor cortex of individuals with AdSD and healthy controls. Considering that rTMS at low frequencies (≤1 Hz) produces lasting inhibition in a process analogous to long-term depression, and that AdSD is associated with decreased cortical inhibition, the purpose of this pilot study is to determine safety, feasibility and response to 1Hz rTMS to the laryngeal motor cortex in individuals with AdSD and healthy people.

2.2 Device Description

We will utilize two Magstim 2002 devices (US FDA #K060847) with a Bistim 70-mm figure-eight coil. rTMS will be delivered with air-film coils (real) and a Magstim Rapid2 device (US FDA #K051864). For data acquisition, the electrode wires will be connected to a bipolar electromyography (EMG) pre-amplifier (Y03, Motion Lab Systems, Inc., LA, USA) with the gain of x300. The EMG signal will be passed through a band-pass filter with the cutoff frequencies of 15Hz and 2000Hz and then digitized by an analog-to-digital convertor (NI 9234, National Instruments Corporation, Austin, TX, USA) with a resolution of 24-bits at a sampling rate of 6400Hz.

Both TMS devices are used for investigational purposes and labeled with the following statement: CAUTION – Investigational Device. Limited by Federal law to investigational use.

2.3 Device Accountability

The device is not supplied to the subject, and will not be in the subject's possession at any time.

3.0 Study Objectives

3.1 Primary Objective

The purpose of this project is to determine safety, feasibility and response to 1Hz rTMS to the laryngeal motor cortex in individuals with AdSD and healthy people. The following Aims will be tested:

Aim 1: Determine safety and feasibility for the application of 1 Hz rTMS to the laryngeal motor cortex.

Hypothesis: rTMS to laryngeal motor cortex will be safe and feasible as measured by no serious adverse events and 100% study completion by participants.

Aim 2: Determine amount of intracortical inhibition in the laryngeal motor cortex as measured in the thyroarytenoid both within and between groups before and after rTMS. Hypotheses:

- The AdSD group will demonstrate less inhibition in the laryngeal motor cortex at baseline.
- rTMS will increase intracortical inhibition for the laryngeal motor cortex in both groups, but AdSD individuals will show greater changes.
- There will be no difference between groups at posttest suggesting a normalizing of intracortical inhibition.

Aim 3: Explore changes in voice quality following rTMS with a blinded assessment by a voice expert.

Hypothesis: Clinical scores will show a trend toward improved voice quality in people with AdSD.

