4.4 Study Population

4.4.1 Sample Size

This is the first pilot study of this kind and, therefore, no data are available for sample size calculation. Data from this pilot study will be used for effect size calculations for future investigations.

We plan to enroll 40 subjects (20 people with AdSD and 20 healthy controls). Due to the voluntary nature of our recruitment efforts, we expect a small number to dropout or fail screening qualifications. To ensure the needed number of enrollees, 50 subjects have been requested to be recruited in our IRB application.

Due to no direct benefit from participation, children will be excluded from this study.

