5.8 Subject Withdrawal

5.8.1 How to Withdraw Subjects

Subjects may be withdrawn from the study for the following reasons:

- o occurrence of intolerable pain or discomfort during testing
- o failure to attend scheduled testing or treatment sessions
- o subject consent withdrawal

In the event of subject withdrawal, all collected data and personal information will be documented and kept private. If a subject is withdrawn from the study, they will keep their identifier code and an additional subject will be recruited to account for the needed subject sample. Withdrawn subjects will be documented and future participants will start at the beginning of the study. Additional subjects will be drawn from the same pool of candidates who expressed interest in the study. The same recruitment procedures and experimental procedures will be followed for all subjects.

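### Aim 1 rests on zero SAEs and 100% completion, but the plan does not say whether replaced subjects or early-stopped sessions count, and Section 6.2 has no Aim 1 analysis

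*Combined protocol and SAP*

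**What the plan says.** The Aim 1 hypothesis in Section 3.1 is that "rTMS to laryngeal motor cortex will be safe and feasible as measured by no serious adverse events and 100% study completion by participants". These are its only two measures.

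The other sections that bear on it are:

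- **Numbers (4.4.1).** "We plan to enroll 40 subjects (20 people with AdSD and 20 healthy controls"); "we expect a small number to dropout or fail screening qualifications"; and so "50 subjects have been requested to be recruited in our IRB application". No dropout rate is given, and dropout is pooled with screen failure. The Study Summary instead says "Fifty participants will be enrolled".
- **Withdrawal (5.8.1).** Reasons include "occurrence of intolerable pain or discomfort during testing" and "failure to attend scheduled testing or treatment sessions". Withdrawn subjects are documented: "they will keep their identifier code and an additional subject will be recruited to account for the needed subject sample".
- **Exit and stopping (4.4.7, 7.2.3).** Completing the protocol is listed as an exit condition, separate from withdrawal and adverse events. A session may be stopped early for an individual subject, and nothing says how that session counts.
- **Analysis (6.1, 6.2).** Section 6.1 covers all subject data, with the purpose of exploring rTMS effects. Section 6.2 gives descriptive statistics for excitability and voice quality. Neither mentions SAEs or completion.
- **Safety capture (Section 7).** AEs and SAEs are defined, recorded, monitored and reported.

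**The concern.** Section 3.1 puts safety and feasibility in the study's purpose, and Section 5.3 gives them as the reason for having no sham arm. The plan still leaves two questions open.

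**Completion.** Each withdrawn subject is replaced until the needed sample is reached, so the same data give two answers. Among the final 40, completion is 100% however many withdrew. Among everyone who began, it is lower. The plan does not say which rate answers Aim 1, so the choice could be made after the data are seen. A subject who withdraws because the procedure was intolerable is the kind of case a feasibility aim should count.

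**Safety.** A count of zero is easy to check, but in a small sample it says little about the underlying rate. Section 7.2.1 cites earlier experience with this type of rTMS. Section 2.1, however, says the team knows of no study that has modulated laryngeal motor cortex excitability. Section 7.2.1 also lists risks of electrode placement, so exposure to risk begins before rTMS.

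**Working it through.** The plan gives no sample-size calculation or expected rate to reproduce, so the check is on what the criterion can show.

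**Inputs from the documents.** Planned sample 40, of whom 20 have AdSD (4.4.1). Recruitment ceiling 50 (4.4.1). Places beyond the planned sample: 50 − 40 = 10, shared between dropout and screen failure. Withdrawn subjects are replaced (5.8.1).

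**Assumptions.** The number of post-screening withdrawals and the true SAE rate are not given, so ranges are shown.

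**Step 1: completion.** With w withdrawals, each replaced, and 40 finally completing, the rate among all who began is 40/(40 + w). The exact (Clopper-Pearson) 95% limits for x of n are Beta quantiles: lower = Beta(0.025; x, n − x + 1), upper = Beta(0.975; x + 1, n − x), with an upper limit of 1 when x = n.

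| Replaced withdrawals w | Among all who began | Exact 95% CI | Among final 40 only |
|---|---|---|---|
| 0 | 40/40 = 100% | 91.2–100% | 100% |
| 1 | 40/41 = 97.6% | 87.1–99.9% | 100% |
| 5 | 40/45 = 88.9% | 75.9–96.3% | 100% |
| 10 | 40/50 = 80.0% | 66.3–90.0% | 100% |

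The last row is an outer bound. It requires every spare place to be a post-screening withdrawal, whereas 4.4.1 expects only a small number of dropouts and screen failures together. The row with w = 1 is enough to make the point.

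**Step 2: zero SAEs.** For 0 events in n, the two-sided 95% upper limit is 1 − 0.025^(1/n), and the one-sided limit is 1 − 0.05^(1/n).

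| n | Two-sided upper limit | One-sided upper limit |
|---|---|---|
| 40 (both groups) | 8.8% | 7.2% |
| 20 (AdSD) | 16.8% | 13.9% |
| 50 (recruitment ceiling) | 7.1% | 5.8% |

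**Step 3: chance of meeting the SAE criterion.** For an assumed true rate p, the chance of no SAE in 40 people is (1 − p)^40.

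- p = 1%: 0.99^40 = 0.669, or 67%
- p = 2%: 0.98^40 = 0.446, or 45%
- p = 5%: 0.95^40 = 0.129, or 13%

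A true SAE rate of 2% would therefore meet the criterion nearly half the time.

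**The case against.** The strongest reply is that this is a descriptive pilot and the sentence is a hypothesis. No decision to proceed, test or progression rule is tied to it, and 4.4.1 gives effect-size calculation for later studies as the use of the data. That stands: a single withdrawal would mean an expectation was not met, and no trial decision would change. It does not remove the gap, because the sentence is the only stated measure of Aim 1.

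Several stronger readings are tempting, and the documents do not support them:

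- **That withdrawn subjects will be dropped from the rate.** No section says so. They keep their codes and are documented, and the natural sense of completion by participants is everyone who took part. The fair complaint is that the denominator is unstated.
- **That completion is wholly undefined.** Much of it can be inferred: there is one session (4.1), an itemised visit (5.5), no follow-up (5.4), and exit conditions that separate completing from withdrawing (4.4.7). The real ambiguity is a session stopped early or a visit with a step missing.
- **That the endpoint list in 4.3 is itself in error.** That section is headed as effectiveness, and safety has its own Section 7. The omission that matters is in 6.2.
- **That safety data will be lost.** Section 7 captures serious and non-serious events.

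It is also true that any 40-person pilot leaves several percent open, and that 5.3 calls the data preliminary. That supports reporting an interval; it does not support treating a zero count as a demonstration of safety.

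**Conclusion.** The concern holds as a gap in the Aim 1 criterion and its analysis. Expected dropout, replacement of withdrawn subjects and a 100% criterion cannot be read together until the plan says who is counted. The choice matters from the first withdrawal: 100% among the final 40 against 97.6% (87.1–99.9%) among all 41. Zero SAEs is compatible with a true rate of up to 8.8% overall and 16.8% in AdSD, so it cannot carry a conclusion of safety unaided.

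The intervals assume independent subjects with a common rate, and that the planned 40 (20 with AdSD) are reached. The withdrawal counts and SAE rates are illustrations. The point should be corrected, but it does not threaten the conduct of the study, since every item needed is already recorded.

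**What to change.** In Sections 3.1 and 6.2:

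1. Replace the all-or-nothing criterion with counts, rates and exact (Clopper-Pearson) 95% intervals for completion and SAEs, overall and for AdSD.
2. Define completion as finishing rTMS and the post-rTMS TMS and voice assessments.
3. Use as the completion denominator all consented subjects who pass on-site screening. Count withdrawn subjects and their replacements, and count a session stopped early as not completed. This is an analysis definition and leaves the stopping rule as it is.
4. Report screen failures and non-attenders separately, with counts. Consent and on-site screening both take place at the single visit (5.5), so these groups can be told apart. A denominator of all consented subjects would also be defensible, provided it is fixed in advance.
5. Report SAEs over everyone who starts any study procedure: electrode placement, TMS or rTMS.
6. State that zero events alone will not be taken to show safety.

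Also align the enrolment figure in the Study Summary (50) with 4.4.1 (40 planned, up to 50 recruited).

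The cost is wording only: no added visits, data or subjects. The downside is that the figures will look less favourable, the AdSD intervals will be wide, and the report can no longer make a simple statement that rTMS was safe and feasible.

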4.0 Study Design

4.1 Overview of Study Design

This experiment is a pilot study involving within and between group comparisons: AdSD compared to healthy controls, before and after rTMS delivery. Participants will be asked to come to the University of Minnesota for 1 session.

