5.2 Allocation Scheme

Individuals will be assigned to each group based on their diagnosis and symptoms. All subjects will be assigned to the same procedures.

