5.3 Clinical Procedures

Clinical assessment: Voice measures consisting of standard and published clinical scales will be collected for all participants to explore changes in voice quality (Zraick *et al.*, 2011; Samargia *et al.*, 2016). Voice quality will be measured by asking subjects to repeat 10 sentences with a high number of initial adductor phonemes, which often elicit symptoms in those with AdSD. These voice samples will be acquired digitally using a microphone. The frequency of voice breaks in the

recorded 10 sentences will be counted. These voice breaks will be the measure of disease severity. Other voice characteristics will be assessed using the Consensus Auditory-Perceptual Evaluation of Voice (CAPE-V) and the Voice Handicap Index (VHI). The CAPE-V is a reliable, valid clinical measure used by voice experts to assess voice quality. During a video recording, participants will be asked to repeat 6 sentences and then describe their voice problems. Voice experts will use the recording to rate voice quality based on several criteria (loudness, pitch, strain, breathiness, roughness, overall severity and others). In the current study, the total score in this scale will be used to rate the voice quality of participants before and after rTMS. The VHI is a self-administered questionnaire with questions about how often a given voice-related problem affects the life of participants. It reliably measures the influence of the subjects' voice disorder on their quality of life across three dimensions including: physical, functional and social. The total score for each participant will be measured before rTMS to assess how the voice disorder affects quality of life.

TMS testing: TMS testing will be performed to measure the corticospinal excitability before and after rTMS. TMS testing will be completed according to established methods (Kimberley and Di Fabio, 2010; Samargia *et al.*, 2014; Kimberley *et al.*, 2015a; Kimberley *et al.*, 2015b). Single and paired-pulse TMS testing will be delivered with a 70-mm figure-of-eight coil connected to a Magstim 200 stimulator (Magstim Company, Dyfed, UK), positioned on the scalp area over the left primary motor cortex. The laryngeal motor cortex will be identified by measuring the motor evoked potentials (MEP) of the thyroarytenoid muscle. Cortical stimulation will be spatially tracked with a neuronavigation system (BrainSight, Rogue Research Inc. Quebec, Canada) to decrease variability of stimulus delivery.

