The TMS variables that will be measured in the study include single pulses that evoke a response in the muscle. The variable of interest is the amplitude of motor evoked potential (MEP) in response to different stimulation intensities and duration of silent period after the evoked response. Testing will include no more than 200 pulses (rTMS delivery will involve 1200 pulses — see below). Overall, the testing procedures will take approximately 60 minutes (30 minutes before and 30 after rTMS).

Fine-wire electrodes: All participants will undergo vocal muscle testing using fine-wire EMG. With the subject seated in a supportive chair, fine-wire EMG electrodes will be inserted in the thyroarytenoid muscles (the "vocal cords") by a trained physician, [name]. The skin on the throat will be numbed using a lidocaine cream and also an injection of a lidocaine (numbing) agent. Once the skin has been numbed, the electrode will be placed into the muscle. To place the electrode, two fine wires will be inserted using a small gauge needle (30MM, 27 guage) with the edges of the wire electrode hooked around the tip of the needle and connected to an EMG machine. The needle will be passed through the skin and into the larynx. When the vocal cord is entered, an increased EMG signal associated with speech is detected. The needle will then be removed, leaving only the flexible wires in place.

Once the needle is removed, participants will not feel the presence of the electrode. Participants will be able to breath, talk and move their head with the electrode in place. At the end of the testing for vocal muscles, the electrodes will be gently pulled out. This process is nearly unnoticeable due to the very small diameter of the wires. Procedures will be the same as previous study (IRB # 0608M91226. Study Title "Pathophysiology of Spasmodic dysphonia: a TMS study").

rTMS application: rTMS will be delivered to the left laryngeal motor cortex with a hand-held figure-of-eight coil positioned over the scalp and connected to a Rapid² magnetic stimulator (Magstim Company, Dyfed, UK). The protocol described below is FDA approved and has been used extensively by our lab without incident. The risk of seizure is minimized by using a low rate of stimulation and a sub-threshold level of intensity.

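### Aim 2 reads equal posttest inhibition as normalizing, but controls receive the same rTMS, so equality need not mean the unstimulated healthy level

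*Combined protocol and SAP*

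**What the plan says.** Section 3.1 gives Aim 2 three hypotheses:

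1. "The AdSD group will demonstrate less inhibition in the laryngeal motor cortex at baseline".
2. "rTMS will increase intracortical inhibition for the laryngeal motor cortex in both groups, but AdSD individuals will show greater changes".
3. "There will be no difference between groups at posttest suggesting a normalizing of intracortical inhibition".

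Section 2.1 rests the rationale on the same comparison of patients with healthy people: "TMS data indicate differences in inhibition in people with AdSD vs. healthy controls". Section 4.1 describes the design as "AdSD compared to healthy controls, before and after rTMS delivery", and section 5.2 adds: "All subjects will be assigned to the same procedures". Section 5.3 gives low-frequency rTMS to every participant, calls it inhibitory, and rules out sham because the study is preliminary.

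Section 6.1 has excitability measured before and after rTMS in everyone. Section 6.2 plans changes from baseline in both groups, summarized descriptively because the sample is unlikely to support formal comparison. No section defines normalizing, sets an equivalence margin, or names a comparison of AdSD after rTMS with controls before it.

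**The concern.** The deficit in the first hypothesis is measured against healthy people who have not been stimulated. The third hypothesis judges its removal against healthy people who have been. By posttest the reference has been moved, on the protocol's own prediction, in the same direction as the patients.

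What is at stake is the wording of the Aim 2 conclusion. The result that best fits the hypotheses would be described as normalizing, although the patients need not be at the healthy level. Excitability is the primary endpoint (4.3.1) and the pilot is meant to supply effect sizes for later studies (4.4.1), so this reading could be carried forward. No test, decision or sample size depends on it. Aim 1, safety and data collection are unaffected.

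**Working it through.** The plan states no effect size, SD, power or margin, so there is no figure of its own to reproduce. The check is algebra on group means, followed by a precision calculation.

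**Notation**
- H: healthy mean at baseline. D: baseline deficit in AdSD, so the AdSD baseline mean is H − D (hypothesis 1: D > 0).
- e: rTMS effect in controls. f: rTMS effect in AdSD (hypothesis 2: e > 0 and f > e).
- s: retest or within-session drift, assumed equal in both groups.

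**Posttest means**
- Controls: H + s + e.
- AdSD: H − D + s + f.
- Unstimulated healthy people measured at the same time would be at H + s. No such group exists.

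**Contrasts**
- Target, AdSD posttest minus unstimulated healthy level: (H − D + s + f) − (H + s) = f − D.
- (i) AdSD posttest minus control baseline: f − D + s.
- (ii) AdSD posttest minus control posttest: f − D − e.
- (iii) Control change: c = s + e, which equals (i) − (ii) when the same controls contribute at both times.

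Contrast (ii) misses the target by e and contrast (i) misses it by s. Setting (ii) to 0 gives f = D + e, which puts the target at e: AdSD ends above the unstimulated healthy level by e, whatever D is. Setting the target to 0 gives f = D and (ii) = −e, so exact return to the healthy level leaves a posttest gap and the third hypothesis fails.

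**Illustration.** All values are assumed, in SD units, with D = 0.8 and posttests equal (f = D + e):

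| e | s | c = s + e | f | (ii) | (i) | Target |
|---|---|---|---|---|---|---|
| 0.3 | 0 | 0.3 | 1.1 | 0 | 0.3 | 0.3 |
| 0.5 | 0 | 0.5 | 1.3 | 0 | 0.5 | 0.5 |
| 0 | 0.5 | 0.5 | 0.8 | 0 | 0.5 | 0 |
| 0.3 | −0.3 | 0 | 1.1 | 0 | 0 | 0.3 |

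In the third row the control change is large, yet the inference is sound because the change is all drift. In the fourth row the control change is zero, yet the inference is wrong. So c does not measure the error.

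**Precision.** With 20 per group (4.4.1) and equal SDs assumed, the 95% CI half-width for (i) or (ii) is t(0.975, 38) × √(2/20) = 2.024 × 0.316 = 0.64 SD. For c it is t(0.975, 19) × √(2(1 − r)/20), where r is the pre-post correlation. For assumed r = 0.3 / 0.5 / 0.7 / 0.8 this gives 0.55 / 0.47 / 0.36 / 0.30 SD. An observed posttest difference of exactly zero would therefore be compatible with true gaps of up to about 0.64 SD in either direction.

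**The case against.** The strongest reply is that the protocol never says normal means unstimulated. Aim 2 and section 4.1 compare the groups before and after under identical procedures. On that reading normalizing describes a move from deficit to no deficit under the same conditions, and the word is neither empty nor wrong. This stands as a possible meaning. It is not stated, though, and the first hypothesis and section 2.1 point to the ordinary healthy level, so the protocol should say which it intends.

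It can also be said that the posttest comparison cancels drift shared by both groups, which a comparison with control baseline does not. That is right, and it is why neither contrast should replace the other. A reader might infer that the third hypothesis fails unless the observed control change is about zero. The documents do not support this: with no sham, that change cannot be divided into rTMS effect and drift.

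A reader might also think that hypotheses 2 and 3 contradict each other. They do not: both hold when f = D + e. The fault lies in the inference attached to the third, not in its prediction.

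Finally, section 6.2 is descriptive, admits the limits of the sample, and already plans change from baseline in both groups. Point estimates of every contrast follow from those summaries. It would go too far to say how often the study would wrongly declare no difference, since the plan contains no rule for declaring it. What remains is that nothing ties the control change, or the comparison with control baseline, to the normalizing statement.

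**Conclusion.** Wrong as written, in interpretation only; minor. If normal means the unstimulated healthy level, lack of a posttest difference does not show normalization, and the error is the rTMS effect in controls. Its existence follows from the protocol's second hypothesis. Its size is not given, and the design cannot isolate it. The algebra holds for any baseline deficit and any AdSD response, provided drift is the same in both groups; unequal drift would add its between-group difference to the error. If rTMS has little effect in controls, the practical consequence is small. If normalizing means only closure of the gap under equal stimulation, the fault reduces to an undefined term.

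The imprecision is a separate limit: about ±0.64 SD for a between-group difference at 20 per group, with equal SDs assumed.

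**What to change.** **Section 3.1, third hypothesis.** Keep the posttest comparison. Either delete the closing clause about normalizing, or restate it as: the baseline gap closes when both groups have received rTMS. Do not replace it with a claim that the gap is smaller at posttest than at baseline, because that largely repeats the greater AdSD change already in the second hypothesis.

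**Section 6.2.** For each inhibition measure analyzed, report with 95% CIs and no test:
- AdSD posttest minus control baseline;
- AdSD posttest minus control posttest;
- the control pre-post change.

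State that the first includes retest and session effects and that the second uses stimulated controls. State also that normalization will not be concluded from lack of a posttest difference alone. Section 5.3 lists "amplitude of motor evoked potential (MEP) in response to different stimulation intensities and duration of silent period after the evoked response" and also mentions paired-pulse testing, without saying which serves Aim 2. The three contrasts apply to whichever inhibition measures are used.

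**Cost.** One edited hypothesis, a few lines in 6.2, and three interval estimates per measure from data already planned. No new participants, visits or procedures. The downside is some added inference in a descriptive pilot, with intervals that are likely to be inconclusive.
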